4. STUDY DESIGN

This survey questionnaire is a cross-sectional study that is limited to National Dental PBRN dentists who are currently practicing. Approximately 4,000 dentists will be invited to participate (approximately 2,400 respondents expected for an anticipated 60% average response rate, or approximately 2,500 maximum should the response rate be higher). All Network members, at the limited or full participation level, who are general dentists or specialists (N~992) in Endodontics, Periodontics, Prosthodontics, Orthodontics, Pediatric Dentistry, Dental Public Health, Orthodontics, and Oral/Maxillofacial Surgery will be invited to participate. Oral Pathologists and Oral Radiologists will **not** be invited to participate, as they are rarely involved with issues regarding AP.

Based on previous survey research within the Network, we anticipate an approximately 60% completion rate on average. Westat Coordinating Center will be responsible for randomly selecting dentists from within each Network region. Network regional quotas will help to ensure that each region has adequate representation within the survey.

Participation involves the completion of the practitioner AP Prescribing Practices survey. Dentists will complete the survey online through the REDCap survey management system, or upon special request a paper version can be mailed by a study team member at the Coordinating Center to the individual through standard United States Postal Service (USPS), and returned to sender upon completion via a pre-stamped, "no postage necessary" envelope that will accompany the hard copy. The return envelopes will be pre-addressed to the attention of [name] (SPI), and data entry will be performed by one of the designated study team members at the Coordinating Center. The paper, or hard, copy of the survey will be identical to the web-based survey. Westat Coordinating Center will be responsible for providing the SPI with contact information (including active email addresses) for member dentists randomly selected for participation based on inclusion/exclusion criteria. Dentists will be invited via email. The AP Prescribing Practices survey data will be collected via an online survey instrument housed in the Carolinas Medical Center (CMC) REDCap survey management system (SMS).

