11.2. Sample Size Considerations

All objectives of the current study are either descriptive or exploratory - rather than hypothesis testing - in nature. Therefore, standard sample size calculations based on anticipated effect sizes do not apply. However, based on a survey quideline report by Brinkman W-P et al.*, our proposed sample size will allow us to perform statistical analyses for observed small to medium effect sizes (comparing general dentists to specialists, all categories included) and for medium to large effect sizes (specialist subcategories). Our sample size was selected based on the total number of dentists available as of January 7th 2017 (N=4002 including 3002 general dentists (GDs) and 992 specialists, excluding the category "other", see Table 1 below). Our 3-pronged recruitment approach will ensure comparable representation of both general and specialist dentists from all National Dental PBRN regions and minimize the margin of error to compare generalists with specialists overall or to compare some of the specialist subcategories (e.g. pediatric dentists vs. non-pediatric specialists). Table 1 below presents National Dental PBRN enrollment data for each region from Jan 7, 2017. Table 2 presents the number of invited participants and anticipated number of completing participants, per each dentist or region category with respective survey margins of error (MOE) at 95% confidence level. Proposed sample size allows for a margin of error of 3.15% (+/- 0.34 (SD)) on average per region (generalists and specialists combined),

0.05% for general dentists and 2.55% for specialists (all regions combined), at 95% confidence level. The online tool (https://www.qualityoutcomes.com/samplesize.aspx) was used to determine whether samples size per region or per specialty were appropriate to allow for minimal MOE possible.

* Preliminary version of: Brinkman, W-P (2009). Design of a Questionnaire Instrument, Handbook of Mobile Technology Research Methods, ISBN 978-1-60692-767-0, pp. 31-57, Nova Publisher.

Table 1. National PBRN Enrollment as of Jan 7th 2017

					Specialists subcategories							
Region	Dentists	Total Dentists	GDs	SPs	Total SPs	Endo-	Pediatric	Perio-	Prostho-	Oral/Maxillo-	Ortho-	
	all PBRN	w/o "Other"			w/o Other	dontist	Dentist	dontist	dontist	facial Surgeon	dontist	
1. Western	599	583	415	184	168	22	21	11	6	7	101	
2. Midwest	494	481	350	144	131	19	23	17	12	8	52	
Southwest	797	783	594	203	189	27	36	43	11	19	53	

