4. South Central	755	744	606	149	138	21	28	27	14	12	36	
5. South Atlantic	585	577	446	139	131	20	20	19	18	4	50	
6. North East	852	834	599	253	235	24	42	37	20	18	94	
Total	4082	4002	3010	1072	992	133	170	154	81	68	386	

 Table 2. Sample size determinations per region and per specialty category (60%) response rate),

 95% confidence level

			Specialists subcategories							
			Total Size	MOE	Endo-	Pediatric	Perio-	Prostho-	Oral/Maxillo-	Ortho-
Region	GDs	Sps	Region	Region	dontist	Dentist	dontist	dontist	facial Surgeon	dontist
1. Western	249	100	350	3.33	13	13	7	4	4	60
2. Midwest	210	79	289	3.65	12	14	10	7	5	31
Southwest	356	113	469	2.87	16	21	26	7	11	32
4. South Central	363	83	446	2.94	13	17	16	8	7	22
5. South Atlantic	268	79	346	3.34	12	12	11	11	3	30
6. North East	359	141	500	2.78	14	25	22	12	11	56
Total Size Cat.	1805	595	2400	1.27	80	102	92	49	41	231
MOE Cat.	0.05	2.55	1.27	-	7.00	6.20	6.59	9.00	10.00	4.10

Final Analysis Plan

Two forms of missing data will be addressed by our analysis of main outcomes. First, we anticipate some degree (approximately 40%) of *total non-response*: dentists sent a unique survey participation link who do not respond/initiate the survey within the study period for a variety of reasons including refusal, non-contact, illness, death, or some other barrier preventing participation. Data missing due to total non-response will be addressed by the following approach: (1) We will describe characteristics of dentists who did not respond to the survey using data from their National Dental PBRN Enrollment Questionnaire; (2) We will then examine and report potential demographic (age, gender, ethnicity) and practice (specialty, practice location, primary practice setting) characteristic differences between respondents and total non-respondents; (3) If significant demographic differences emerge between respondents and non-respondents, sample-

weighting adjustments will be applied to the data; and (4) Main outcomes will be analyzed using both non-weighted and weighted datasets.

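### Non-response weighting is triggered by demographic differences only, so a response imbalance confined to specialty, practice location or setting is reported but leads to no adjustment

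*Protocol*

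**What the plan says.** The rule is in the Protocol under Final Analysis Plan (11.3 in the table of contents), where total non-response is handled in four steps. About 40% non-response is expected; Section 4 gives the complement: "we anticipate an approximately 60% completion rate on average".

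- Step (1) describes non-respondents from their Enrollment Questionnaire data.
- Step (2) examines "potential demographic (age, gender, ethnicity) and practice (specialty, practice location, primary practice setting) characteristic differences between respondents and total non-respondents". The parentheses define two distinct sets.
- Step (3) is conditional: "If significant demographic differences emerge between respondents and non-respondents", then sample "weighting adjustments will be applied to the data". Only the first set is named, and the variables that would form the weights are not listed.
- Step (4) states: "Main outcomes will be analyzed using both non-weighted and weighted datasets".

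Section 11.2 justifies the sample size partly by "comparing general dentists to specialists, all categories included", and by comparisons among specialist subcategories. Table 2 applies one 60% response rate to every dentist category.

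**The concern.** Step (2) separates demographic from practice characteristics, and step (3) carries only the demographic set forward. An analyst who follows the text could find a large difference in response by specialty, report it, and have no instruction to adjust for it. Step (4) does not help in that case, because no weighted dataset would have been created.

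This matters because the survey is descriptive. Its main products are estimated proportions, and with about 40% of invitees expected not to respond, non-response is a leading threat to them. If specialists and general dentists differ in beliefs or prescribing, a distorted specialty mix shifts any estimate pooled over all dentists. A distorted mix of subspecialties does the same to any estimate for specialists as a group. A larger sample does not reduce either shift.

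**Working it through.** **Inputs from the Protocol.** Table 1, excluding the category Other: 3,010 general dentists, 992 specialists (386 of them orthodontists), 4,002 in total. The text of Section 11.2 gives 3,002 general dentists; 3,010 is used here because 4,002 − 992 = 3,010. Table 2: 1,805, 595 and 2,400 expected respondents; margins of error 1.27 (overall) and 2.55 (specialists).

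**Reproducing the stated figures.**

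- Respondents at 60%: 3,010 × 0.6 = 1,806; 992 × 0.6 = 595.2; 4,002 × 0.6 = 2,401.2. These agree with Table 2 up to rounding.
- Overall margin: 1.96 × √(0.25/2,400) = 2.00 points; times the finite-population factor √((4,002 − 2,400)/4,001) = 0.633, this gives 1.27.
- Specialist margin: 1.96 × √(0.25/595) = 4.02 points; times √((992 − 595)/991) = 0.633, this gives 2.54 (stated 2.55).

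**Bias formula.** Bias = (group's share among respondents − its share in the frame) × (difference in the outcome between that group and the rest). With equal response the shares match and the bias is zero.

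**Pooled estimate.** The frame share of specialists is 992/4,002 = 24.8%. Specialist response rates and outcome differences below are assumptions; overall response is held at 60%.

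| Specialist response | General dentist response | Specialist share of respondents | Bias, 10-point difference | Bias, 30-point difference |
|---|---|---|---|---|
| 40% | 66.6% | 16.5% | −0.8 | −2.5 |
| 50% | 63.3% | 20.7% | −0.4 | −1.2 |
| 70% | 56.7% | 28.9% | +0.4 | +1.2 |
| 80% | 53.4% | 33.1% | +0.8 | +2.5 |

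First row: 0.40 × 992 = 396.8; 396.8/2,401.2 = 16.5%; 16.5 − 24.8 = −8.3 points; × 0.30 = −2.5.

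**Specialist estimate.** The frame share of orthodontists among specialists is 386/992 = 38.9%. With overall specialist response held at 60%:

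- Orthodontist response of 40%: 154.4/595.2 = 25.9%, a shift of −13.0 points.
- Orthodontist response of 80%: 308.8/595.2 = 51.9%, a shift of +13.0 points.
- Resulting bias: 1.3 points for a 10-point outcome difference and 3.9 points for a 30-point difference.
- At 50% or 70% response the corresponding figures are 0.65 and 1.95.

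**Would step (2) notice?** For 63.3% against 50%: z = 0.133/√(0.6 × 0.4 × (1/3,010 + 1/992)) = 0.133/0.0179 ≈ 7.4. The imbalance would be plain, yet step (3) would not act on it.

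**Cost of weighting on specialty alone.** The variance inflation from unequal weights is (n/N²) × Σ(N_h²/n_h).

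- Specialist response of 50%: (2,401.2/4,002²) × (3,010²/1,905.2 + 992²/496) = 1.01.
- Specialist response of 40%: (2,401.2/4,002²) × (3,010²/2,004.4 + 992²/396.8) = 1.05.

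**The case against.** **Loose wording.** The word demographic in step (3) may be shorthand for both sets just listed. That is plausible, and would make this a drafting slip. But step (2) defines the terms separately in the sentence before, and nothing else in the Protocol triggers weighting on a practice difference.

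**Specialty might still be corrected.** A reader might infer that specialty imbalance can never be adjusted for. The Protocol does not support that: the weighting variables are not named, so specialty could enter once a demographic difference had triggered weighting. That would be incidental.

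**Recruitment already balances the sample.** Sections 4, 5.3 and 6.1 describe regional quotas and waves adjusted to response, and Section 11.2 expects comparable representation of general dentists and specialists. This is a partial answer. The stated mechanism is mainly regional, no specialty quota is given, and inviting about 4,000 of a frame of 4,002 leaves almost no reserve.

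**The stated comparison is not affected.** A reader might infer that unequal response by general dentists and specialists biases the contrast between them. It does not, by itself; each group's own estimate is unaffected by the other's response rate. The contrast is exposed only through imbalance within a group, such as the subspecialty mix.

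**The size is assumed.** This stands. At specialist response of 50% or 70% the pooled bias stays below 1.27 even with a 30-point difference. Without the finite-population factor the margin would be about 2.0, which only the extreme cases exceed.

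**The rest may belong to an analysis plan.** A reader might also object that a significance test is a poor trigger that will sometimes fire by chance, or that having two sets of results invites selection. Little harm follows here. Chance weighting costs only some variance, the survey is declared descriptive or exploratory, both analyses are promised, and a separate plan may name the main one.

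**Conclusion.** The point holds in limited form. As written, a difference in specialty, practice location or practice setting does not trigger non-response weighting, although the Protocol requires these differences to be examined. The estimates at risk are those pooled over all dentists and, through the subspecialty mix, those for specialists as a group.

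The figures assume that response departs from 60% by 10 to 20 points in the affected group and that outcomes differ by 10 to 30 points. On that basis the pooled bias is about 0.4 to 2.5 points against a stated margin of 1.27. The specialist estimate moves by about 0.65 to 3.9 points against a stated 2.55. The Protocol supplies neither response rates nor outcome differences by specialty, so these figures show what is possible and do not predict what will happen. The effect is negligible if response is similar across specialties.

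Severity is moderate: a stated rule that should be corrected before analysis, but not one that undermines the survey.

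**What to change.** Rewrite step (3) so that non-response weights are always computed, whatever the significance tests show. Weight respondents to the known enrollment-frame margins for specialty, region, practice location, practice setting, age, gender and ethnicity. Continue to report weighted and unweighted results, preferably with the weighted result as the main one.

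At minimum, extend the trigger in step (3) to demographic or practice differences, and state that the practice variables enter the weights.

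The cost is a change of wording and modest analysis work. Step (1) already relies on Enrollment Questionnaire data for non-respondents, so no new data collection should be needed. The downside is some loss of precision: about 1% to 5% more variance for weighting on specialty alone in the two cases worked above, and somewhat more as further variables are added.

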12. SOURCE DOCUMENTS AND ACCESS TO SOURCE DATA / DOCUMENTS

Only study personnel (i.e., NND, SPI, Co-I's, RCs, CC personnel) will have access to the study data elements in the study databases (as described below). Source data for the study consist of the following: (1) Practitioner data from the Enrollment Questionnaire; and (2) Practitioner responses to the electronic AP Prescribing Practices survey.

Enrollment Questionnaire Data. Enrollment Questionnaire data will be provided to the SPI by the Westat Coordinating Center. Enrollment questionnaire data will be provided in a separate file from identifying/contact information. The contact information file and the Enrollment Questionnaire data file will be linked by the use of unique participant IDs. A file linking participant IDs with identifying information will be stored electronically in a password protected file on the CMC secure server network. The contact information file will be used as the basis for communication of study completion status between the SPI and the RCs. Password protected recruitment logs will be shared with RCs via the secure CMC file sharing service on a regular (approximately weekly) basis.

REDCap Practitioner Survey. Dentist participants will directly enter all practitioner survey data into the REDCap SMS. REDCap survey data will be stored in a coded dataset through the use of unique participant IDs.

Survey Closeout. Following close of survey enrollment, a cleaned and completed survey dataset will be merged with participants' selected Enrollment Questionnaire data provided by Westat at the outset of study implementation. A final, merged, cleaned, and coded dataset will be delivered to Westat for archival following the closeout of the study. In addition, the SPI will deliver a Study Participation report to Westat documenting the completion status of participants (e.g., complete, incomplete, refused, ineligible).

13. QUALITY CONTROL AND QUALITY ASSURANCE

For the QA/QC activities associated with data collection and processing, the SPI will specify which data QA/QC procedures will be provided. The procedures will include the development of automatic data quality checks in the SMS for the survey and the processes related to the data manual review, discrepancy management, data verification and approval, and database audit. The REDCap survey will be programmed with edit checks and response limiters to reduce data response errors.

The SPI will ensure that the electronic surveys are being collected appropriately and confidentially and will ensure completeness of data collected. Conference calls with the Study Team (and relevant RCs) will be held at least monthly during the practitioner questionnaire data collection phase to monitor recruitment progress and data completeness and troubleshoot any problems that may arise.

14. ETHICS / PROTECTION OF HUMAN SUBJECTS

14.1. Ethical Standard

The GPI, SPI, and Co-Investigators will ensure that this study is conducted in full compliance with the principles set forth in The Belmont Report: Ethical Principles and Guidelines for the Protection of Human Subjects of Research, as drafted by the US National Commission for the Protection of Human Subjects of Biomedical and Behavioral Research (April 18, 1979) and codified in 45 CFR Part 46.

14.2. Institutional Review Board

The UAB IRB for Human Use serves as the National Dental PBRN Central IRB and will review this protocol. If the local institution has decided to use the National Dental PBRN Central IRB review, the National Dental PBRN Central IRB is the IRB responsible for the review of the protocol. The National Dental PBRN Central IRB would then perform all future continuing protocol reviews and amendment (new protocol version) reviews. The Central IRB would also review unanticipated problems distributed by the Administrative Unit to local institution PIs.

Local institutions have the prerogative to use the National Dental PBRN Central IRB review or conduct their own local review. If a Regional Administrative Site (RAS) or other local institution elects not to use the National Dental PBRN Central IRB, the protocol, consent form(s) or waiver if warranted, recruitment materials and all participant materials will be submitted to the RAS or other local institution IRB (e.g. CMC) for review and approval. Approval (either centrally for those regions who agree to central approval, or regionally for those who do not) of both the protocol and the consent form must be obtained before any participant is enrolled. Any amendment to the protocol will require review and approval by the IRB before the changes are implemented in the study.

14.3. Informed Consent Process

A waiver of documentation of signed informed consent for practitioners who complete the electronic survey questionnaire will be requested. Consistent with regulations outlined by the National Dental PBRN Central IRB and CMC IRB, information about the study will be provided to eligible practitioners in an initial study invitation email as well as in the electronic questionnaire

prior to the start of the survey questions. Completion of the survey will provide a record of tacit consent.

14.4. Exclusion of Women, Minorities, and Children (Special Populations)

Racial and ethnic minorities are invited to participate in the study at least proportional to the composition in National Network dental practitioner membership. Individuals of any gender or racial/ethnic group may participate.

14.5. Participant Confidentiality

Practitioner confidentiality is strictly held in trust by the study investigators, study staff, and the sponsor(s) and their agents. The study protocol, documentation, data, and all other information generated will be held in strict confidence. No information concerning the study or the data will be released to any unauthorized third party without prior written approval of the sponsor. Westat, who will be responsible for ensuring dental professionals completing the survey are remunerated \$50, will be provided limited, but necessary survey data to fulfill the responsibility of appropriately directing practitioner payments to their desired address.

Participants will be assigned a unique identification number, which will be used to maintain study records and organize data transcripts. The study monitor or other authorized representatives of the sponsor may inspect all study documents and records required to be maintained by the study site.

15. DATA HANDLING AND RECORD KEEPING

The study team is responsible for ensuring the accuracy and completeness of the data collected. Only study personnel (i.e., GPI, SPI, Co-I's, RCs, CC personnel) will have access to the study data elements in the study database as described in *Section 15.3 Types of Data*. Study personnel will include those who are on the approved IRB study protocol. All study personnel will have completed the required training elements for human subjects research certification.

15.1. Data Management Responsibilities

Data collection and accurate documentation are the responsibility of the study staff. Dentist participants will directly respond to the electronic survey through the REDCap SMS, or return completed paper survey to sender. CMC will serve as the Data Coordinating Center (DCC) and will provide data management services for this study. The Carolinas Healthcare System Information Security Management Program (ISMP) is a multi-layered security program designed to provide in-depth defense that models that of the National Institute of Standards and Technology Cybersecurity Framework (NIST CSF). The NIST CSF was designed as a scalable cybersecurity framework based upon existing standards and best practices.

Carolinas Healthcare System (CHS) ISMP is designed to meet the regulatory requirements of the Health Insurance Portability and Accountability Act (HIPAA), the Health Information Technology for Economic and Clinical Health (HITECH) Act, the Payment Card Industry Data Security Standards (PCI-DSS), and the North Carolina Identity Theft Protection Act. A Chief Information Security Officer (CISO) oversees the ISMP. CHS also has a dedicated team of Information Security (IS) professionals to manage day-to-day operations of the program. CHS IS Team is responsible for ensuring that all computer systems containing confidential data pertaining to this project have the level and scope of security that meets, or exceeds, that established by the HIPAA Security Rules and the Office of Clinical and Translational Research (OCTR) at CHS.

The CMC data center in which the REDCap servers are housed has strict access control; rejecting and banning IP addresses of any user that is suspicious. Thresholds of use are set by administrators such that, should they be met, the user will be immediately and permanently banned from the application/server. All transactions are securely delivered to the application using SSL (SHA-1 with RSA Encryption; 2048-bits). It is then transmitted internally (behind the firewall) to the database server. All transactions are logged at the server layer, application layer, and the database layer. Access to the data is managed by institutionally sponsored login IDs. All passwords for registered users are salted and are unrecoverable once created. REDCap administrators are also automatically alerted if normal user activity is potentially destructive to collected data within individual data repositories so that it may be prevented and the user directly notified.

While REDCap provides the capacity to program response limiters (to prevent impossible responses, reduce typos), study personnel will review data weekly to identify impossible values, outliers, and missing data. Following close of survey enrollment, a cleaned and completed survey dataset will be merged with dental participants' selected Enrollment Questionnaire data provided by the CC at the outset of study implementation.

